## **Protocol Synopsis**

**Title:** A RaNdomized Double-bIInd Placebo ConTrolled Study Characterizing THe Effects of PCSK9 Inhibition On Arterial Wall inflammation in Patients with Elevated Lp(a) (ANITSCHKOW)

**Study Phase:** 3b

**Indication:** Hyperlipidemia

### **Primary Objective:**

- To evaluate the effect of evolocumab on arterial wall inflammation, as measured by percent change from baseline in target-to-background ratio (TBR) of an index vessel by fluorodeoxyglucose-positron emission tomography/computed tomography (FDG-PET/CT) at week 16 in subjects with baseline lipoprotein (a) [Lp(a)]  $\geq$  50 mg/dL and low density lipoprotein-cholesterol (LDL-C)  $\geq$  100 mg/dL

[figure not shown]
### **Secondary Objectives:**

- To evaluate the effect of evolocumab on Lp(a), as measured by percent change from baseline at week 16 in subjects with baseline Lp(a)  $\geq$  50 mg/dL and LDL-C  $\geq$  100 mg/dL
- To evaluate the effect of evolocumab on LDL-C, as measured by percent change from baseline at week 16 in subjects with baseline Lp(a)  $\geq$  50 mg/dL and LDL-C  $\geq$  100 mg/dL
- To evaluate the effect of evolocumab on Apolipoprotein B (ApoB), as measured by percent change from baseline at week 16 in subjects with baseline Lp(a)  $\geq$  50 mg/dL and LDL-C  $\geq$  100 mg/dL

**Safety Objective:** To evaluate the safety of evolocumab in subjects with baseline Lp(a)  $\geq$  50 mg/dL and LDL-C  $\geq$  100 mg/dL

### **Exploratory Objectives:**

CCI

**Hypotheses:** The primary clinical hypothesis is that administration of evolocumab 420 mg subcutaneous (SC) monthly will result in greater change from baseline TBR at week 16 than placebo in subjects with elevated baseline Lp(a).

**Primary Endpoint:** Percentage change from baseline in TBR within the MDS of the index vessel (right carotid, left carotid, or thoracic aorta) by FDG-PET/CT at week 16.

[figure not shown]
### **Secondary Endpoint(s):**

- Percentage change in Lp(a) from baseline at week 16
- Percentage change in LDL-C from baseline at week 16
- Percentage change in ApoB from baseline at week 16

**Safety Endpoints:** Subject incidence of treatment-emergent adverse events compared to placebo for the duration of the study

**Exploratory Endpoints:**

CCI

**Study Design:** This is a phase 3b, multi-center, double-blind, randomized, placebo-controlled study evaluating the effect of evolocumab on arterial wall inflammation as measured by FDG-PET/CT following 16 weeks of treatment in subjects with elevated levels of Lp(a).

**Sample Size:** Approximately 120 subjects will be enrolled in the study.

**Summary of Subject Eligibility Criteria:** The study will enroll adult subjects ( $\geq 50$  years of age) with elevated levels of lipoprotein(a) and LDL-C and TBRmax  $> 1.6$  of (carotid arteries or aorta) by FDG-PET/CT. Those subjects receiving lipid-lowering therapy (not required), including statin, must be on a dose that remained unchanged for  $\geq 8$  weeks prior to screening. For a full list of eligibility criteria, please refer to [Section 4.1](#).

**Investigational Product (IP):** Evolocumab or matching placebo administered by prefilled autoinjector (AI)/pen

**Amgen Investigational Product Dosage and Administration:**

Evolocumab 420 mg or matching placebo will be administered once monthly (QM) for 12 weeks as a SC injection with a total volume of 3.0 mL, via 3 separate autoinjections of 1.0 mL. The SC injections with the AI/Pen should be administered in a consecutive fashion with all injections completed within 30 minutes.

**Procedures:**

After subjects complete the informed consent form, they will be screened. Two screening visits (screen 1 and screen 2) will be conducted. Subjects should complete all the required tests and procedures in screen 1 and the site will confirm that the subject meets the inclusion criteria based on these procedures before the subject proceeds to the procedures in screen 2.

Screening evaluations will include complete medical and medication history; vital signs; physical examination; measurement of body weight, waist circumference, and height; and laboratory tests (fasting lipids, Lp(a), chemistry, estimated glomerular filtration rate, hemoglobin A1C, and, if applicable, serum pregnancy and follicle-stimulating hormone). FDG PET/CT will be conducted at the screen 2 visit. Subjects will receive a placebo administration with three 1.0 mL SC injections with the prefilled AI/Pen to confirm tolerance of SC administration at the screen 2 visit (considered the placebo run-in). At this time, the subject will receive instruction/training on AI/Pen use. The maximum total screening period is 56 days, including both screen 1 and screen 2.

Subjects who meet all eligibility criteria at the end of the screening period will be randomized and will return within 3 days of randomization for day 1 procedures. Those subjects receiving lipid lowering therapy (not required to participate in this study) will continue to receive the same dose of their background lipid-lowering treatment during the entire time of screening and throughout the study.

Baseline evaluations will be performed on day 1 of treatment before subjects receive the first dose of investigational product. Laboratory tests will be conducted at day 1 (fasting lipids, Lp(a), OxPL/ApoB, IL-6, hsCRP1, biomarkers, hematology, urinalysis, and Lp(a) isoform number, hematology, and urinalysis) and week 8 (fasting lipids and Lp(a)). Adverse events, serious adverse events, adverse device effects (ADE)s, disease-related events, and changes in concomitant medications will be recorded at each visit. At the end of study visit at week 16,

---

FDG-PET/CT and laboratory tests (fasting lipids, Lp(a), OxPL/ApoB, IL-6, hsCRP1, biomarkers [serum, plasma and cell], and Lp(a) isoform number) will be conducted and adverse events, serious adverse events, ADEs, disease-related events, and changes in concomitant medications will be recorded.

[figure not shown]
The overall study design is described by a [study schema](#) at the end of this synopsis section. For a full list of study procedures, including the timing of each procedure, please refer to [Section 7](#) and the Schedule of Assessments ([Table 1](#)).

**Statistical Considerations:** The superiority of evolocumab to placebo will be assessed for all efficacy endpoints on the full analysis set (FAS), which includes all randomized subjects who receive at least one dose of IP. The primary endpoint is the percentage change from baseline in MDS TBR at week 16. Percentage change for MDS TBR will be modeled as an analysis of covariance (ANCOVA) model with the treatment group and the stratification factor in the model. FDG-PET/CT observations made after an on-study cardiovascular event will be included in the primary analysis, and a sensitivity analysis excluding these observations will be conducted. To handle missing data, the correlations between the model errors as well as baseline values of MDS TBR and Lp(a) (and on-study percent change from baseline in Lp(a)) will be modeled. Analysis of the secondary endpoints Lp(a), ApoB and LDL-C will use a repeated measures model on the FAS including terms for treatment group, stratification factors, scheduled visit, and the interaction of treatment with scheduled visit. Safety endpoints will be summarized descriptively by treatment group. For a full description of statistical analysis methods, please refer to [Section 10](#).

---

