### 7.2.3 Treatment

Visits will occur per the Schedule of Assessments ([Table 1](#)) during the treatment period from day 1 (week 1, baseline) through week 12. Visits during the treatment period must be completed within  $\pm$  7 days of the target visit date.

Evolocumab/placebo is to be administered at the site after blood draw procedures. IP administration should be the last procedure to be performed during each visit.

If a subject withdraws from the study early, all efforts should be made to complete and report the observations as thoroughly as possible up to the date of withdrawal. The procedures for the EOS visit should be completed at the time of withdrawal ([Section 7.2.4](#)).

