#### **7.2.4 End of Study Visit**

At week 16, subjects will return to the site for the EOS visit for the procedures specified in the Schedule of Assessments ([Table 1](#)).

End of Study is defined as the date when the last subject has completed all planned study procedures up to and including the EOS visit as outlined in the Schedule of Assessments ([Table 1](#)).

Subjects who do not complete their EOS visit and assessments are considered early termination. Subjects who terminate the study early prior to week 12 will not be eligible to perform the final FDG-PET/CT imaging.

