### 10.2 Sample Size Considerations

At present, PCSK9 inhibitors have not been evaluated for their ability to lower arterial wall inflammation. Therefore, we have used an efficacy study with atorvastatin aimed to lower LDL-C and arterial wall inflammation for our sample size estimation (Tawakol et al, 2013). The planned sample size is 120 subjects (60 in evolocumab and 60 in control). Based on Tawakol et al 2013, we make an assumption that each 10% reduction in LDL-C results in an approximate reduction of 2.4% in MDS TBR. Further assume that 70% of the subjects will be on a statin and 30% will not be on a statin. From the results of the phase 3 evolocumab studies, a treatment effect of evolocumab QM over placebo in the percentage reduction in LDL-C at week 16 is assumed to be 55% for subjects who are not on a statin and 60% for patients who are on a statin. From the assumption that 10% of LDL-C reduction induces an approximate 2.4% of TBR reduction, we expect to observe a combined reduction of 14.0% in MDS TBR at week 16 in the evolocumab

group compared to the control group. A combined standard deviation of 20.0% for the percentage change from baseline to week 16 is assumed for MDS TBR. After accounting for a dropout rate of 25%, the power is greater than 90% for testing superiority of evolocumab over placebo on the percentage change in MDS TBR at week 16.

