10.5.1 Analyses of Primary Efficacy Endpoint

10.5.1.1 Primary Analysis of Primary Endpoint

The primary endpoint is the percentage change from baseline in MDS TBR at week 16. In order to estimate the difference in mean percentage change from baseline in MDS

TBR and to handle missing data for the primary endpoint, a multivariate regression model will be used. The response variables are percent change from baseline in MDS TBR at week 16, baseline MDS TBR, percent change from baseline in Lp(a) at weeks 8 and 16, and baseline Lp(a). Each response follows its own regression model:¹

- Percent change in MDS TBR will be regressed on treatment group and the stratification factor (on a statin, not on a statin);
- Baseline MDS TBR will be regressed on the stratification factor (on a statin, not on a statin);
- Percentage change in Lp(a) will be regressed on the treatment group, stratification factor (on a statin, not on a statin), visit, and treatment group by visit;
- Baseline Lp(a) will be regressed on the stratification factor (on a statin, not on a statin).

The variance-covariance matrix of the error terms from the response variables in the multivariate regression will be estimated. This analysis will use the FAS.

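### Missing week-16 MDS TBR is recovered from Lp(a) as the only on-study information, although the sample size assumes that TBR follows LDL-C; LDL-C should be added to the joint model, with a sensitivity analysis for unscanned subjects who stopped drug

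*Protocol*

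**What the plan says.** Protocol 10.5.2 and SAP 10.5.1.1 fit one multivariate regression, with handling of missing primary-endpoint data as a stated purpose. The responses are week-16 percent change in MDS TBR, baseline MDS TBR and the Lp(a) terms (SAP: "percent change from baseline in Lp(a) at weeks 8 and 16, and baseline Lp(a"). The synopsis gives the same list: "baseline values of MDS TBR and Lp(a) (and on-study percent change from baseline in Lp(a)) will be modeled". LDL-C is not a response, and nor is whether the subject had stopped drug.

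Protocol 10.2 and SAP 3.2 build the effect size on LDL-C: "we make an assumption that each 10% reduction in LDL-C results in an approximate reduction of 2.4% in MDS TBR". From that, "we expect to observe a combined reduction of 14.0% in MDS TBR at week 16".

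Four further rules decide who has blood results but no scan, and which results count:
- Protocol 6.2.1.2: a subject who stops IP for intolerance still returns for all other procedures until end of study.
- Protocol 7.2.4: "Subjects who terminate the study early prior to week 12 will not be eligible to perform the final FDG-PET/CT imaging".
- Protocol 7.2.3, for early withdrawal: "The procedures for the EOS visit should be completed at the time of withdrawal".
- SAP Appendix B: lipids and Lp(a) from after day 1 up to day 84 are assigned to week 8, and the record nearest day 57 is kept.

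Table 1 of the protocol has fasting lipids and Lp(a) at the same visits. The sensitivity analyses of the primary endpoint (SAP 10.5 table and 10.5.1.2) are the exclusion of scans after a cardiovascular event, an Lp(a) covariate, and subgroups. None addresses missing TBR. For missing Lp(a), a secondary endpoint, SAP 10.5.2 plans two imputations for subjects who discontinued IP.

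**The concern.** Efficacy is analysed by randomized group, so an evolocumab subject who stopped drug counts in the evolocumab mean. If that subject has no scan, the model predicts the TBR change from the subject's arm and from the other responses. The only one of these that can show that drug was stopped is Lp(a) change.

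Lp(a) is the weaker marker on the plan's own figures: an effect of about 28% (Protocol 2.3) against a planned LDL-C effect of 58.5%. If TBR change follows LDL-C, as the sample size assumes, a return of Lp(a) to baseline moves the predicted TBR only a little. The subject then keeps most of the on-drug effect and the treatment difference is too large. At stake is a bias in the primary estimate that favours evolocumab, while a collected variable that could reduce it goes unused.

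**Working it through.** **Inputs from the documents.** 60 per arm; effect 14.0 points; SD 20.0 ("A combined standard deviation of 20.0% for the percentage change from baseline to week 16 is assumed for MDS TBR"); 25% dropout; LDL-C effect 60% on statin and 55% off statin, mixed 70/30; 0.24 points of TBR per point of LDL-C; Lp(a) effect about 28%.

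**Assumed, because the documents do not give them.** Two-sided alpha 0.05; within-arm SD 20 for both lipid changes; within-arm LDL-C/Lp(a) correlation r = 0.4 (range 0.2 to 0.6); lipids back at baseline when off drug; the 0.24 ratio also holding between subjects within an arm.

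**1. The plan's own figures reproduce.** LDL-C effect = 0.7 × 60 + 0.3 × 55 = 58.5. TBR effect = 0.24 × 58.5 = 14.04. Evaluable per arm = 60 × 0.75 = 45. SE = 20 × √(2/45) = 4.22. Power = Φ(14/4.22 − 1.96) = Φ(1.36) ≈ 91%, which agrees with the stated figure above 90%.

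**2. Effect credited by the planned model.** Within-arm slope of TBR on Lp(a) = 0.24 × r × (SD LDL-C / SD Lp(a)) = 0.24 × 0.4 × 1 = 0.096. A 28-point return of Lp(a) removes 28 × 0.096 = 2.69 points. The subject is still credited with 14.04 − 2.69 = 11.35 points, or 81% of the effect. The true value under the premise is 0.

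**3. Bias in the treatment difference.** Bias = (share of the evolocumab arm that is off drug, unscanned and has an off-drug sample) × 11.35. With 25% of 60, 15 scans are missing in the arm.

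| Affected of 60 | Share | True difference | Planned model | Bias |
|---|---|---|---|---|
| 3 | 5% | −13.3 | −13.9 | 0.6 |
| a quarter of 15 | 6.25% | −13.2 | −13.9 | 0.7 |
| half of 15 | 12.5% | −12.3 | −13.7 | 1.4 |
| all 15 | 25% | −10.5 | −13.4 | 2.8 |

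For half of 15, r = 0.2 gives 0.125 × (14.04 − 1.34) = 1.6 and r = 0.6 gives 0.125 × (14.04 − 4.03) = 1.25.

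**4. With LDL-C in the model.** If the sample was taken off drug, the prediction is −14.04 + 0.24 × 58.5 = 0, and the bias goes.

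**5. Which sample is retained.** This decides how much of step 4 is realised. A joint normal model was fitted to 100,000 simulated subjects. TBR followed LDL-C, and 10% or 25% of subjects were off drug and unscanned. Lipid SDs were 20 to 25 and the LDL-C/Lp(a) correlation 0.2 or 0.5; baseline responses and the statin factor were left out. Share of the on-drug effect credited:

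| Lipid samples available | Planned | With LDL-C |
|---|---|---|
| Off-drug at week 16, or at weeks 8 and 16 | 73–98% | about 0% |
| Left early, off-drug week-8-window sample only | 82–95% | about 20% |
| Left early, on-drug sample only | about 100% | about 100% |

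**6. Full five- versus eight-response models.**
- Retained week-8 sample on drug: −13.9 without LDL-C, −14.0 with it (truth −12.4).
- Retained week-8 sample off drug: −13.9 without, −12.8 with (truth −12.5).
- Subject-level slope 0.06 in place of 0.24: −13.9 without, −13.5 with (truth −12.3).

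The SE rose by 0 to about 2.5%.

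**The case against.** The strongest reply has four parts.

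- **Few subjects may be affected.** Stopping drug does not by itself lose the scan. The rule that withholds it covers only those who leave the study before week 12, and the 25% is a dropout allowance for sample size. This stands: the documents do not say how many subjects are off drug, unscanned and sampled off drug.
- **The informative sample may be discarded.** For someone who leaves before week 12, Appendix B keeps the record nearest day 57. That will usually be the scheduled week-8 sample, taken after doses at day 1 and week 4, rather than a later withdrawal sample. This also stands. LDL-C then helps mainly subjects who left before their week-8 visit, or who stayed for later bloods but missed the scan.
- **The 0.24 ratio is used only to project a group effect.** It need not hold between subjects within an arm. With half of 15 affected, r = 0.4, the same 14-point effect and a within-arm slope of 0.12, adding LDL-C moves the estimate from −13.9 to −13.2 (truth −12.3), which is under half of the bias.
- **The trial is about Lp(a).** Its title, rationale and hypothesis make Lp(a) a reasoned choice of auxiliary. If TBR followed Lp(a) at 0.5 point per point, the planned model would credit about 0% when off-drug samples exist at weeks 8 and 16. This defends keeping Lp(a) but not leaving LDL-C out, since the proposal keeps every Lp(a) response.

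A reader might also infer that Lp(a) is the only source for recovering missing TBR. It is not, because baseline MDS TBR is a response too; Lp(a) is the only on-study source.

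**Conclusion.** The point holds as a conditional one. Lp(a) change is the only on-study information used to recover missing TBR, LDL-C is collected at the same visits but unused, and no sensitivity analysis covers missing TBR. If TBR follows LDL-C, unscanned evolocumab subjects who are off drug are credited with most of the on-drug effect. The bias is about 0.5 to 1.5 points in favour of evolocumab over plausible assumptions, against an SE of about 4. If all 15 missing evolocumab scans came from such subjects it would be about 2.8, which is an upper bound and not a forecast.

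Two stronger readings are not supported:
- **That the plan does credit stoppers with most of the effect.** This depends on within-arm quantities that are not documented. With share credited = 1 − ρ × (20 / SD of Lp(a) change) × (28/14), where ρ is the within-arm TBR/Lp(a) correlation, the share falls below 50% once ρ exceeds 0.25 (SD 20) to 0.375 (SD 30). The LDL-C premise with the assumed SDs implies ρ of only about 0.05 to 0.15.
- **That adding LDL-C removes the bias.** The underlying cause is a missing-at-random fit by randomized arm that does not know who stopped drug. LDL-C helps only as far as the retained sample was taken off drug.

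What remains is a cheap improvement worth making.

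**What to change.** 1. In SAP 10.5.1.1, Protocol 10.5.2 and the synopsis, add two sets of responses: percent change in LDL-C at weeks 8 and 16 (regressed on treatment group, statin factor, visit, and treatment by visit) and baseline LDL-C (regressed on the statin factor). Keep all Lp(a) responses. The treatment coefficient in the MDS TBR equation stays the primary estimate.
2. In SAP 10.5.1.2, add a sensitivity analysis of the primary endpoint for subjects who stopped IP and have no scan. It should mirror SAP 10.5.2: one imputation with mean zero change, and one from subjects in the same arm who stopped IP and were scanned, if there are enough of them. This covers the bias that LDL-C cannot reach.

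**Cost.** Wording only, settled before unblinding, with no new samples, visits or subjects. Covariance parameters rise from 5 × 6 / 2 = 15 to 8 × 9 / 2 = 36 with about 120 subjects. The SE rose by up to about 2.5% in simulation, and the larger model was not materially worse in any scenario run. Naming the five-response model as the fallback if the larger one does not converge would guard against that risk.

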**Sponsor: Amgen Inc.**

Data Element Standards                    5: 20 March 2015  
Version(s)/Date(s):

## Study Glossary

Abbreviation or Term	Definition/Explanation
ADE	adverse device effect
AE	adverse event
AI	autoinjector
ALP	alkaline phosphatase
ALT	alanine aminotransferase
ANCOVA	analysis of covariance
Apo(a)	apolipoprotein(a)
Apo(B)	apolipoprotein(B)
AST	aspartate aminotransferase
CHD	coronary heart disease
CI	confidence interval
CRF	case report form
CT	computed tomography
CTCAE	common terminology criteria for adverse events
DILI	drug induced liver injury
DRE	disease-related event
EDC	electronic data capture
eGFR	estimated glomerular filtration rate
End of Study (end of trial)	defined as the date when the last subject has completed all planned study procedures up to and including the End of Study visit as outlined in the Schedule of Assessments
End of Study (primary completion)	defined as when the last subject is assessed or receives an intervention for the purposes of final collection of data for the primary endpoint(s)
End of Study for Individual Subject	defined as the last day that protocol-specified procedures are conducted for an individual subject
End of Treatment	defined as the last assessment for the protocol-specified treatment phase of the study for an individual subject
EOS	end of study
FAS	full analysis set
FDG	fluorodeoxyglucose
FDG-PET/CT	fluorodeoxyglucose-positron emission tomography/computed tomography
FSH	follicle-stimulating hormone
GCP	Good Clinical Practice
HDL-C	high-density lipoprotein cholesterol
hsCRP	high sensitivity C-reactive protein

Abbreviation or Term	Definition/Explanation
ICF	informed consent form
ICH	International Conference on Harmonisation
IL-6	Interleukin-6
IMP	investigational medicinal product
INR	international normalized ratio
IP	investigational product
IPIM	Investigational Product Instruction Manual
IRB/IEC	institutional review board/independent ethics committee
IVRS	interactive voice response system, telecommunication technology that is linked to a central computer in real time as an interface to collect and process information.
IWRS	interactive web response system
LDL-C	Low-density lipoprotein-cholesterol
LDLR	low-density lipoprotein receptor
Lp(a)	lipoprotein(a)
MDS	most diseased segment
NSAID	nonsteroidal anti-inflammatory drug
OxPL	oxidized phospholipids
PCI	percutaneous coronary intervention
PCSK9	proprotein convertase subtilisin/kexin type 9
QM	once monthly
SAE	serious adverse event
SC	subcutaneous
Source Data	information from an original record or certified copy of the original record containing patient information for use in clinical research. The information may include, but is not limited to, clinical findings, observations, or other activities in a clinical trial necessary for the reconstruction and evaluation of the trial. Source data are contained in source documents (original records or certified copies). (ICH Guideline (E6)). Examples of source data include Subject identification, Randomization identification, and Stratification Value.
Study Day 1	defined as the first day that protocol-specified investigational product(s)/protocol-required therapies is/are administered to the subject
SUV	standardized uptake value
TBL	total bilirubin
TBR	target-to-background ratio
ULN	upper limit of normal

